# Unanticipated risks:

Any experiment may involve risks that cannot be anticipated. Any identified risks will be reported immediately to UTSW IRB for further consideration.

# 11. Subject Safety and Data Monitoring:

All HD-tDCS sessions will be overseen by the Co-PIs. All safety precautions recommended by scientific literature and the UT Southwestern IRB will be carefully followed. All adverse events volunteered by the subject or elicited by the research team will be recorded in the subjects' research file. All adverse events will be reported within one week to the IRB. Any severe adverse events will be

reported within 24-48 hours to the IRB. Data safety monitoring and review will be performed every six months by the research team.

In order to safeguard our participants from a breach in confidentiality, the data is coded with a unique semi-random subject identifier (URSI). All data after initial entry into the study is coded based on the participant's number. A digital file containing completed questionnaires and assessments from the experimental session will be maintained with the URSI number. These files will be stored on password in a locked cabinet in a secure location (physical data) and accessible only to study personnel. The people who will have access to the data include members of the research team. Identifiable data will not be shared with investigators outside of the research team. The data is also available to the IRB for audit purposes. Other investigators at UTSW wishing to do secondary analysis may have access to the data.

#### 12. Procedures to Maintain Confidentiality:

Confidentiality will be maintained according to the highest standards. All subjects will be assigned a unique research identifier number (ID). All data will be deidentified with this ID and recorded on subject case report forms. The case report forms and key for linking coded identifiers to personal identifiers will be maintained in an encrypted UTSW IRB approved electronic data management program and on password protected computers that only designated study personnel have access to. Research data created by this study will not become part of hospital or institutional medical records. Study personnel are not obligated to share study results with the participant.

The UTSW IRB that oversees human subject research will be permitted to access participant records. There may be times when we are required by law to share our study participant's information. However, the name of the participant will not be used in any published reports about this study. A copy of the consent form will be kept in a locked cabinet in a secure location (physical data) that is password protected and accessible only to study personnel. The study data may also be presented at meetings, published in journals/books or used in classrooms for training purposes. It is possible that these data may be used for testing various future analysis tools, in hopes of finding better ways to understand the results.

Finally, the participant will understand that the investigator is not prevented from taking steps, including reporting to authorities, to prevent serious harm to himself or herself or to others.

# 13. Potential Benefits:

The potential benefit of this study to subjects includes the opportunity to contribute to a scientific investigation that may benefit others in the future. Benefits to others include: informing a possible new intervention for cognitive deficits in TBI. The risks associated with study procedures are no more than what would be expected in routine clinical and neuropsychological assessment and HD-tDCS applications. Thus, there is a strong benefit to risk ratio. The potential benefits to TBI subjects, scientific community, and society outweigh the risks associated with study procedures.

# 14. Biostatistics:

Mixed effects models will be used to evaluate if active HD-tDCS is associated with significant improvements over sham stimulation in neuropsychological assessments. Changes in performance from baseline to immediately post intervention (cognition in Hypothesis I) and baseline to the 2 month follow-up (Hypothesis II) will be assessed for each neuropsychological outcome measure. To test Hypotheses I and II, interaction effects among treatment group (active and sham) and time will be examined. Statistical significance will be set at a = .05. Covariates of interest include: age, sex, ethnicity, education, use of cholinesterase inhibitors, and assignment phase. Correlation coefficient across time is assumed around 0.6-0.7 based on the literature.

Specifically, we will model each measure at the jth assessment time post-treatment from an individual subject in the ith treatment condition,  $y_{ij}$ , as  $y_{ij}=\mu 0+I(x)\cdot\mu ij+I(z)\cdot dij+eij0$ , where  $\mu 0$  is the baseline mean prior to random assignment to i=1,2 conditions (1- active, 2- sham); µij is the mean change from baseline for j=1,2 assessment times (1- immediate- [T1], 2- eight weeks [T2] post-treatment); I(x)is an indicator variable for phase 1; similarly, I(z) is an indicator for Phase 2 (sham-to-active vs activeto-sham conversion); and dij is the mean change from baseline for j =3,4 assessment times (3immediate- in phase 2, 4- eight weeks [T'2] post-treatment in phase 2). Additionally, eij0 is a random error term with *i*0=0,1,2,3,4, indicating baseline, post-assessment times for both Phases 1 & 2. Phase 1 & 2 errors between subjects are independent but positively correlated within subjects across time; additionally, a consequence of Phase 2 is that Phase 2 errors are positively correlated across the treatment conditions. Due to expected attrition, which will cause missingness in some (but not all) assessment times, and due to the complexity of the constraints, phases, and covariance parameterization in the linear mixed effects model above. all fixed-effect parameter estimates will be obtained by maximum likelihood and all covariance parameters for random effects will be obtained by restricted maximum likelihood (REML). All hypothesis tests will be based on t-statistics from a priori hypotheses, which are interaction contrasts of the form  $(\mu 1j + d1j)/2 - (\mu 2j + d2j)/2$  where j is understood to reflect the same assessment time regardless of phase (i.e., immediate post- OR 8 weeks post-treatment). The interaction contrast, shown above, reflects overall active HD-tDCS effects compared to sham. All analyses will be performed in SAS, R, and/or Matlab.

Mixed effects models will be used to evaluate if active HD-tDCS is associated with significant changes over sham stimulation in EEG measures. Changes from baseline to immediately post intervention (Hypothesis I - latency; Hypothesis II - magnitude) and then baseline to 2 month follow-up (Hypothesis III) will be assessed. To test Hypotheses I-III, interaction effects among treatment group (active and sham) and time will be examined. Statistical significance will be set at a = .05. Correlation coefficient across time is assumed around 0.6-0.7 based on the literature.

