#### The University of Texas Southwestern Medical Center at Dallas Institutional Review Board

#### Protocol

# Using High Definition transcranial Direct Current Stimulation to Treat Verbal Retrieval Deficits Secondary to Chronic Traumatic Brain Injury (HDtDCS-CTBI)

#### 1. Introduction and Purpose:

The pre-supplemental motor area (preSMA) has been shown to play a role in memory and word retrieval. Prior studies have suggested that neurostimulation targeting this region can improve word retrieval as well as other cognitive skills. Entraining the preSMA circuits with 10 sessions of neurostimulation could be used to improve cognitive functioning evaluated by EEG-based and neuropsychological measures. The purpose of this study is to examine the efficacy of high-definition transcranial direct current stimulation (HD-tDCS) to the preSMA region and its influence on EEG and neuropsychological measures in patients with chronic TBI. We also use MRI imaging to examine how baseline white matter integrity affects HD-tDCS therapeutic effects. The 3 aims of this study are 1) to determine HD-tDCS targeting pre-supplementary motor area (pre-SMA) modulatory effects on verbal retrieval function and synchronized brain activity using electroencephalography (EEG), 2) to use MRI imaging to examine how baseline white matter integrity affects HD-tDCS therapeutic effects. Herapeutic effects, and 3) to establish predictive models of HD-tDCS induced changes by integrating baseline EEG and MRI measures.

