#### 2. Background:

High Definition transcranial Direct Current Stimulation (HD-tDCS) represents a safe, portable, and low-cost noninvasive brain stimulation technology to target more focused brain regions and modulate dysfunctional brain circuitry underlying neurocognitive symptoms. The pre-Supplementary Motor Area (pre-SMA) is part of the neural circuit underlying word retrieval functioning and can be more easily modulated by HD-tDCS than other deeper brain structures in the circuit. We have shown in pilot studies that adults with word retrieval impairment long after traumatic brain injury (TBI) can have enhancement of word retrieval from HD-tDCS targeting the pre-SMA. Immediately following stimulation, active HD-tDCS compared to sham was associated with significant improvement on a verbal (semantic) fluency task in a small sample of adults (N=25). We later combined neuropsychological and EEG measures in a case study of a patient with word retrieval impairment 3 years after a severe TBI, and found that HD-tDCS to the pre-SMA led to enhancement of verbal (phonemic) fluency (named 36 more items than baseline) and improved frontal EEG activity that lasted for 2 months. Thus, our preliminary work indicates HD-tDCS may have the potential to improve word retrieval functioning in those with chronic TBI and that HD-tDCS induced improvement could persist for 2 months

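### No primary outcome and no error control: every cognitive score is tested twice at .05, so a null treatment would show a false benefit in about 12–22% of trials (assuming five scores)

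*Combined protocol and SAP*

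**What the plan says.** The Introduction gives the aim as a test of efficacy: "The purpose of this study is to examine the efficacy of high-definition transcranial direct current stimulation (HD-tDCS". Section 14 then asks whether active stimulation is "associated with significant improvements over sham stimulation in neuropsychological assessments". Change to the immediate post-treatment visit (Hypothesis I) and to 2 months (Hypothesis II) "will be assessed for each neuropsychological outcome measure". The threshold is "Statistical significance will be set at a = .05".

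The same section asks whether active stimulation is "associated with significant changes over sham stimulation in EEG measures", separating latency from magnitude at the immediate visit and adding the 2-month follow-up as Hypothesis III, again at .05. On pre-specification it says "All hypothesis tests will be based on t-statistics from a priori hypotheses" and gives the form of the contrast.

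Section 3 (Study Procedures) lists five skill areas for the battery but no count of scores. The sample size justification claims adequate power for all outcomes alike, at an unadjusted 0.05. No section names a primary outcome, ranks the measures, orders the tests or adjusts for their number, and nothing labels the study exploratory.

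**The concern.** Every score at either time is an equal route to an efficacy claim, each at the full .05. The chance that at least one comes out favourable by luck grows with the number of tests.

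Calling the hypotheses a priori does not limit this. It fixes the form of the contrast, but each neuropsychological hypothesis still covers every measure. The pilot work does not single out a score either. Section 2 (Background) reports "significant improvement on a verbal (semantic) fluency task in a small sample of adults (N=25") and, separately, a phonemic fluency gain in one case study.

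These documents therefore leave open which score and which time decide efficacy, and that could be settled after results are seen. The trial expects about 24 completers, so a single chance finding could carry the report.

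**Working it through.** **The plan's own figure.** The sample size justification states N = 20, power 0.80, alpha 0.05 and f = 0.27 for the treatment-by-time interaction. Take two groups, three times and correlation 0.6 (the lower end of the 0.6–0.7 in Section 14):

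- λ = f²·N·m/(1−ρ) = 0.0729 × 20 × 3 / 0.4 = 10.9, on 2 and 36 degrees of freedom.
- Power is 0.817, so the figure reproduces. It uses an unadjusted 0.05 for every outcome.

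**Inputs for the error rate**

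- From the documents: .05 per test, two times per measure, and correlation across time of 0.6–0.7 (midpoint 0.65 used).
- Assumed: five scores (one per skill area), two-sided tests, and between-score correlation of 0, 0.3, 0.5 or 0.7.
- A false improvement is a statistic above +1.96 under the null. One test gives 2.5%.

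**Correlation between the two times' contrasts**, under compound symmetry with a shared baseline mean and ρ = 0.65:

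- Arms switch in Phase 2 (study overview and the Section 14 model): the within-person contrasts are y1−y3 and y2−y4, with covariance ρ−ρ−ρ+ρ = 0, so the correlation is 0.
- Phase 1 only: ρ/(1+ρ) = 0.65/1.65 = 0.39.
- Same condition in both phases (text under the sample size justification): 2ρ/(1+2ρ) = 1.30/2.30 = 0.57.
- Upper bound: 0.65.

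**Result.** Chance of at least one false improvement in 5 × 2 = 10 tests (multivariate normal simulation, 400,000 draws):

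| Between-time correlation | Between-score 0 | 0.3 | 0.5 | 0.7 |
|---|---|---|---|---|
| 0 | 22.3% | 19.9% | 17.4% | 14.2% |
| 0.39 | 21.1% | 18.8% | 16.3% | 13.4% |
| 0.57 | 20.3% | 17.7% | 15.4% | 12.6% |
| 0.65 | 19.6% | 17.2% | 14.9% | 12.1% |

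Check for independent tests: 1 − 0.975¹⁰ = 22.4%. Simulated trials with 12 per arm and t-tests gave about 13–22%. Relative to one test, 12/2.5 ≈ 5 and 22/2.5 ≈ 9.

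**Sensitivity to the number of scores**, over the same correlations:

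| Scores (each at two times) | At least one false improvement |
|---|---|
| 1 | 4.3–5.0% |
| 2 | 7–10% |
| 5 | 12–22% |
| 10 | 17–40% |

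**EEG, either direction (single test 5%).** Two quantities at two times give 14–19%. If the three quantities implied by Section 8 (frontal latency, left fronto-temporal latency, theta power) are scored separately for each of the two EEG tasks in Section 3, there are 12 tests and about 27–46%; the top is 1 − 0.95¹² = 46%. The count is not stated, so these figures are only indicative.

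**The case against.** The strongest reply is that the percentage is not a property of the plan: the number of scores, the sidedness and the between-score correlation are all supplied from outside. The 22% end needs uncorrelated cognitive scores from the same people. That is fair, and the range should be read as an illustration.

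Second, the focus on verbal retrieval is strong. It appears in the title, in Aim 1 and in the Section 6 entry criteria. If only the two fluency types from the pilot work counted, the figure would be 7–10%. But the focus stops at a domain, and Section 14 extends the same test to every measure. Even one score at two times gives 4.3–5.0% against 2.5%.

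Third, Hypotheses I and II could be treated as separate families. Within one of them, five independent scores give at most 1 − 0.975⁵ = 12%. That halves the maximum but leaves it well above 2.5%, and the plan does not say that the families are separate.

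Fourth, a record outside these documents might fix the outcome. That cannot be seen here; the finding is that the protocol and SAP text do not.

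The documents conflict on whether arms switch in Phase 2, and those passages must be reconciled. This point does not depend on it: the two readings differ by about 2 percentage points.

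**Conclusion.** The concern holds. That no primary outcome, testing order or adjustment is named is a matter of record in the text. Its size is conditional. With five scores, two-sided tests, between-score correlation of 0–0.7 and between-time correlation of 0–0.65, the chance of a false improvement on at least one cognitive test is about 12–22%, some five to nine times that of a single test. With two scores it is 7–10%; with ten, 17–40%. The EEG tests come on top.

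This does not bias any single estimate. It does weaken any efficacy claim that rests on whichever score and time reach .05. The plan should be changed.

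**What to change.** Amend Section 14, with a matching line in its EEG paragraph, before any outcome data are examined. That includes the interim EEG power analysis planned at half recruitment.

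1. Name one specific word-retrieval score from the trial's own battery, chosen by the sponsor, at the immediate post-treatment visit, as the single primary test at two-sided 0.05.
2. Test the same score at 2 months only if the first test is significant.
3. List every other neuropsychological and EEG score and label it secondary.
4. For the secondary scores, state one rule: either Holm within each family, or reporting with confidence intervals as not supporting an efficacy claim.

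The primary test then carries 2.5% false improvement, and the 2-month step adds under 0.1 point. With Holm on the other eight neuropsychological tests, the chance of any false improvement across primary and secondary neuropsychological tests is about 4–5%. Holm by family does not control the trial-wide rate: with six EEG tests added (16 in all, either direction), it falls from 31–56% to 9–14%.

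The cost is wording only, with no loss of power for the primary test. Under Holm, a secondary score with 80% power at 0.05 (expected statistic 1.96 + 0.84 = 2.80) has at the first step:

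- eight tests, 0.05/8 = 0.00625: P(Z > 2.73 − 2.80) ≈ 53%;
- six tests, 0.05/6 = 0.0083: P(Z > 2.64 − 2.80) ≈ 56%.

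Under the no-claim option, secondary tests keep their power but cannot carry an efficacy claim.

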# 3. Study Procedures:

# **Overview and design**

We plan to recruit at least 24 English-speaking participants aged 18-85 years with a history of chronic TBI (> 1 year since injury), all of whom have problems with cognition. Participants will be randomized into an active HD-tDCS condition or a sham condition in order to assess the efficacy of HD-tDCS on improving cognition. The proposed study will measure response to HD-tDCS treatment over the preSMA region when compared to sham. Participants will receive two phases of 10 sessions of active stimulation (1 mA anodal HD-tDCS targeting preSMA for 20 min) or sham across 2 weeks. All participants will be blinded to their condition. EEG and neuropsychological tasks will be completed at

baseline, immediate follow-up after session 10, and a 2-month follow-up. Those participants randomized into the active or sham group will have the opportunity to return after 2 months and receive sham (if active first) or active (if sham first) treatment and will undergo the EEG and neuropsychological tests again immediately following the last HD-tDCS session and at a 2-month follow-up. With this design, we expect a 15% attrition rate and plan on enrolling ~30 adults to achieve our completed sample of 24.

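### If Phase 2 is a crossover, the pooled contrast understates the active effect unless nothing carries over differentially and the effect is equal in both phases; the plan states neither condition (minor)

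*Combined protocol and SAP*

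**What the plan says.** Section 14 (Biostatistics) models each outcome as a change from one baseline taken before randomisation. The mean changes are μ_ij in Phase 1 and d_ij in Phase 2, with i coded 1 for active and 2 for sham ("random assignment to i=1,2 conditions (1- active, 2- sham"). It then fixes the test: "All hypothesis tests will be based on t-statistics from a priori hypotheses", all of the form (μ1j + d1j)/2 − (μ2j + d2j)/2, where j is the same post-treatment time in either phase. It interprets the result without condition: "The interaction contrast, shown above, reflects overall active HD-tDCS effects compared to sham".

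The same section describes Phase 2 as a "sham-to-active vs activeto-sham conversion". The design overview in Section 3 agrees: participants "will have the opportunity to return after 2 months and receive sham (if active first) or active (if sham first) treatment". The visit description under the sample size justification instead has each group repeat its Phase 1 condition. Table 1 lists sham or active for Visits 14–22 but only active for Visit 23.

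On persistence, Section 14 plans to test the change from "baseline to the 2 month follow-up (Hypothesis II"), and Section 2 says that "HD-tDCS induced improvement could persist for 2 months". No section mentions carryover or washout. Assignment phase appears only as a covariate, and Table 1 shows no new baseline before Phase 2.

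**The concern.** In a crossover, the Phase 2 sham mean comes only from people who had active stimulation in Phase 1. The plan hopes to show benefit at 2 months, and 2 months is also the earliest point at which Phase 2 may open. If that hope is borne out, some benefit may still be present when these people serve as the sham comparison. Because d_ij is measured from the pre-randomisation baseline, any residual enters the Phase 2 sham mean in full. An assignment-phase covariate removes a shift common to both sequences, but not a residual confined to one of them.

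At stake is the size of the reported effect. A reader told that the contrast is the overall active effect would take a diluted figure at face value, and the plan commits to no other estimate to set beside it.

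**Working it through.** **1. The plan's own figure.** The sample size justification states that 20 participants give 80% power for a Phase 1 treatment-by-time interaction of f=0.27. With the noncentral F test, two groups, m assessments and λ = f²·N·m/(1−r):
- m=3, r=0.6: λ = 0.0729×20×3/0.4 = 10.935, power 0.817
- m=2, r=0.7: λ = 0.0729×20×2/0.3 = 9.72, power 0.838

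So N=20 reproduces within the correlation range of 0.6–0.7 in Section 14. It concerns Phase 1 alone, and carryover does not affect it.

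**2. What f=0.27 means as a difference in change.** With two groups and two times, f = D/4, so D = 4×0.27 = 1.08 SD. Check at N=20, r=0.7: D² / [2×2(1−r)/10] = 1.1664/0.12 = 9.72, the same λ as above. The plan's d ≈ 0.54 is 2f, which is half this difference in change.

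**3. Expected value of the contrast.** Take i as the condition received. Let P1 and P2 be the phase effects, D the active effect in both phases, and c the share of D still present in the active-first group in Phase 2.

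| Cell | Mean change |
|---|---|
| μ1 (active, Phase 1) | P1 + D |
| μ2 (sham, Phase 1) | P1 |
| d1 (active, Phase 2; sham-first group) | P2 + D |
| d2 (sham, Phase 2; active-first group) | P2 + cD |

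Phase 1 gives D and Phase 2 gives D(1−c). The average is **D(1−c/2)**: 1.00D, 0.875D, 0.75D, 0.625D and 0.50D at c = 0, 0.25, 0.5, 0.75 and 1. Simulation (20,000 trials, 12 per arm, r=0.65, D=0.54) gave means of 0.541, 0.472, 0.404, 0.338 and 0.270, as the formula predicts.

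Two refinements follow. Equal carryover in both sequences cancels, so only differential carryover matters. Absence of carryover is also not sufficient: with c=0 and a Phase 2 effect of 0.5D, the contrast is (D + 0.5D)/2 = 0.75D.

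**4. How plausible is c?** The documents give no value. The claim of persistence to 2 months rests on a "case study of a patient with word retrieval impairment 3 years after a severe TBI". The affected assessments come later than that: at least 8 weeks of follow-up plus 2 weeks of Phase 2 sessions is about 10 weeks after the last active session, and a further 8 weeks makes about 18. A later return makes both longer.

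**5. Precision** (12 per arm, r=0.65, complete data, SD units).
- Pooled: SE = √[2(1−r)/24] = √(0.70/24) = 0.171
- Phase 1, baseline-adjusted: SE = √[2(1−r²)/12] = √(1.155/12) = 0.310

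**6. Power of the pooled test** (two-sided 5%, 22 df, effect D(1−c/2), SE 0.171).

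| D (SD) | c=0 | c=0.25 | c=0.5 | c=1 |
|---|---|---|---|---|
| 0.54 | 86% | 75% | 62% | 33% |
| 1.08 | >99% | >99% | 99% | 86% |
| 1.20 | >99% | >99% | >99% | 92% |

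At r=0.6 the D=1.20, c=1 entry is 88%.

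**The case against.** Three stronger readings are tempting, and the documents do not support them.

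*That i is undefined, or stays with the randomised arm.* The coding is introduced alongside random assignment, so a reader might infer that i follows the arm into Phase 2, in which case the formula would no longer measure active against sham. But Section 14 calls i the treatment condition and codes it active or sham. It also treats subjects as independent while allowing Phase 2 errors to correlate between conditions, which is possible only if one person contributes to both. The contrast's label points the same way. A clarifying sentence is useful, but the meaning is recoverable.

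*That the trial loses its power.* The fall from 86% to 33% applies at D=0.54, half the difference in change that f=0.27 implies. At 1.08 SD the loss is negligible through c=0.5.

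*That carryover creates false positives.* If stimulation has no effect at any time, nothing carries over and the test keeps its 5% level. That assurance is for the global null only. A delayed effect with no immediate effect could reach the Phase 2 immediate assessment; there it would raise the sham mean and push the contrast against active stimulation.

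The other side has two fair points that stand. The value of c is unknown and the evidence for it is thin. And the Phase 1 contrast is a blunt check: its SE of 0.31 exceeds the bias of 0.135 (0.54×0.25) at D=0.54, c=0.5. That argues for reporting it as a sensitivity estimate, not for replacing the pooled test. The whole point is also conditional: if Phase 2 repeats the same condition, this dilution does not arise.

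**Conclusion.** The concern holds as a minor point about interpretation. Under a crossover, with i as the condition received, the sole prespecified contrast equals the active-versus-sham effect only with no differential carryover and an equal effect in both phases. Otherwise it is too small, by c/2 under carryover: 12.5% at c=0.25, 25% at c=0.5, and at most 50% for c between 0 and 1.

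This rests on an assumed c, a common D in both phases, and Phase 2 being a crossover as Sections 3 (overview) and 14 describe. The power figures further assume 12 completers per arm, equal correlation across times and complete data. The test, the stated N=20 and the pooled analysis itself need not change.

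**What to change.** First reconcile the design overview, the visit description, Table 1 (Visit 23) and Section 14 on what Phase 2 delivers. If it is a crossover, add to Section 14:

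> In μ_ij and d_ij, i is the condition received in that phase. The pooled contrast is the test; it equals the active-versus-sham effect only if there is no differential carryover from Phase 1 and the effect is the same in both phases. The Phase 1 contrast μ1j − μ2j, which is free of carryover, will be reported with a 95% interval beside the pooled contrast for each outcome and assessment time, as a sensitivity estimate of the effect size. No carryover test will be used to choose between them, and the conclusion on the presence of an effect follows the pooled test.

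The cost is wording only: no new data, no change to the test, and both contrasts come from the planned model. The downside is that the Phase 1 interval is nearly twice as wide (0.310/0.171 ≈ 1.8), so it may include zero when the pooled test is significant. The last sentence of the proposed text settles that case in advance.
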